4 STUDY POPULATION

4.1 Research Subject Selection

Healthy volunteers will be recruited for this study.

4.2 Recruitment

Volunteers will be recruited through the posting of advertisements, NIH Clinical Research Volunteer Program, and the Subject Recruitment and Referral Center, and they may include NIH employees. All flyers and advertisements will be submitted to the NIAID IRB for approval.

4.2.1 Participation of NIH Employees

NIH employees may participate in this study, with the following conditions:

- Neither participation nor refusal to participate in this protocol will have any effect on the subject's employment or work situation.
- A brief medical exam and medical history will be required for participation in this study along with giving blood and urine specimens. To protect the privacy and confidentiality of employee's participation the employee participant must not work directly for the PI or any of the Associate Investigators on this protocol.

4.3 Inclusion Criteria

1. Age ≥ 18 years and ≤ 60 years
2. Body mass index (BMI) of 19-32 kg/m²
3. Estimated glomerular filtration rate ≥ 70 mL/min at screening, calculated using the CKD-EPI formula
4. Subjects must agree to:
 - Not take any prescription or OTC medications with the exception of acetaminophen, ibuprofen, vitamins, seasonal allergy medications, and/or contraceptive medications for a period 7 days prior to study drug administration (i.e., Day 0)
5. One of the following in order to avoid pregnancy:

- Females who are able to become pregnant (i.e., are not postmenopausal, have not undergone surgical sterilization, and are sexually active with men) must agree to use at least 2 effective forms of contraception from the date of the subject's signing of the informed consent form through 60 days after the last dose of study drug. At least one of the methods of contraception should be a barrier method.
- Males who have not undergone surgical sterilization and are sexually active with women must agree to use condoms plus have a partner use at least one additional effective form of contraception from the date of the subject's signing of the informed consent form through 60 days after the last dose of study drug.

4.4 Exclusion Criteria

1. Any history of allergy, anaphylaxis, or severe reaction to beef products (including milk and gelatin)
2. Any history of allergy, anaphylaxis, or severe reaction to IGIV or human blood products
3. Any chronic medical problem that requires daily oral medications (except Tylenol, ibuprofen, oral contraceptives, vitamins, and seasonal allergy medications).
4. History of cardiovascular disease, cardiomyopathy, heart failure, or unexplained syncope
5. Subjects that have had confirmed MERS
6. Women who are breast-feeding
7. Positive urine or serum pregnancy test
8. Abnormal chemistry panel
 - defined as any clinically significant baseline Grade 1 or greater toxicity, or any Grade 3 or greater toxicity (regardless of clinical significance) by the toxicity table
 - evaluating only sodium (Na), potassium (K), serum bicarbonate (total CO₂), blood urea nitrogen (BUN), creatinine, glucose, asp (ALT), aspartate aminotransferase (AST), total bilirubin, lactate dehydrogenase (LDH), and estimated glomerular filtration rate (GFR) by the CKD-EPI equation.
9. Abnormal complete blood count (CBC)
 - defined as any clinically significant baseline Grade 1 or greater toxicity, or any Grade 3 or greater toxicity (regardless of clinical significance) by the toxicity table
 - evaluating only the WBC (to include absolute neutrophil, lymphocyte, and eosinophil counts), hemoglobin, hematocrit, and platelets.
10. Abnormal urinalysis
 - defined as any clinically significant baseline Grade 1 or greater toxicity

- evaluating only protein, and RBCs
- 11. Positive rheumatoid factor
- 12. IgA deficiency (defined as IgA < 7 mg/dL)
- 13. Participation in another research study with receipt of any investigational drug within 5 half-lives or 30 days, whichever is longer, prior to study drug administration (i.e., Day 0) and until completion of the study
- 14. Participation in any other research study for 30 days after study drug administration
- 15. Receipt of blood products within 2 months prior to study drug administration (i.e. Day 0)
- 16. Receipt of any vaccination within 30 days prior to study drug administration (i.e. Day 0)
- 17. Any acute or chronic condition that, in the opinion of the Investigator, would limit the subject's ability to complete and/or participate in this clinical study

4.5 Justification of Exclusions of Pregnant Women and Children

4.5.1 Exclusion of Pregnant and Breastfeeding Women

Pregnant women are excluded from this study because the effects of SAB-301 on the developing human fetus are unknown with the potential for teratogenic or abortifacient effects. Because there is an unknown but potential risk for adverse events (AEs) in nursing infants secondary to treatment of the mother with SAB-301, women that are breastfeeding will also be excluded from the study.

4.5.2 Exclusion of Children

Because there are insufficient data regarding dosing or AEs events available in adults to judge the potential risk in children, children are excluded from this study.

4.6 Subject Withdrawal

Subjects (or their legal surrogates if subjects become unable to make informed decisions) can terminate study participation at any time without prejudice. If a subject terminates participation before completing the study, the reason for this decision will be recorded in the study record.

Best efforts will be made to follow withdrawn subjects who have received study drug administration for safety. Subjects who withdraw from the study after study drug administration will not be replaced.

4.7 Discontinuation of Subject by Investigator

The Investigator has the right to withdraw subjects from the study. Subjects may be withdrawn from the study for any of the following reasons:

- The subject is lost to follow-up.
- The Investigator believes that continuation in the study would be detrimental to the subject. In general, subjects withdrawn for AEs will still be followed for safety follow-up if possible.
- If, in the Investigator's best judgment, discontinuation is in the subject's best interest.

The reason for withdrawal from the study is to be recorded in the study record. If a non-serious AE is unresolved at the time of discontinuation, efforts should be made to follow up until the event resolves or stabilizes, the subject is lost to follow-up, or there is some other resolution of the event. The Investigator should make every attempt to follow all SAEs to resolution.

Subjects withdrawn from the study after study drug administration will not be replaced.

4.8 Discontinuation of Study

The National Institute of Allergy and Infectious Diseases (NIAID) Office of Clinical Research Policy and Regulatory Operations (OCRPRO) as the study sponsor, the NIAID Institutional Review Board (IRB), and the Food and Drug Administration (FDA) may terminate this study at any time. Reasons for terminating the study may include, but are not limited to, the following:

- The incidence or severity of an AE in this or other studies indicates a potential health hazard to subjects.
- Subject enrollment is unsatisfactory.
- Data recording is inaccurate or incomplete.
- Investigators do not adhere to the protocol or applicable regulatory guidelines in conducting the study.

4.9 Emergency Unblinding

If a subject experiences a SAE, and the treating clinician requests unblinding of the study treatment, the Principal Investigator (PI) or designee will be contacted. If the PI or designee is in agreement that unblinding is necessary, the PI or designee will contact the NIH Clinical Center Pharmacy for release of the randomization code for the subject to the treating clinician. The sponsor, Medical Monitor, and DSMB will be informed within one business day that unblinding was necessary. In this case, the subject is still considered enrolled in the study, and the data is still used for analysis.

5 TREATMENT

5.1 Randomization and Blinding

A blinded randomization scheme will be generated by the NIH Clinical Center Pharmacy prior to the initiation of the study.

The pharmacy order will be entered into Clinical Research Information System (CRIS), and at this time, the subject will be assigned a randomization code by pharmacy, which is the next unassigned number in the randomization scheme.

Study participants and study team (PI and associate Investigators and study staff) will be blinded throughout the entire study. The study team will be unblinded after the Study Day 90 visit, all laboratory (and immunogenicity) results are available, and the final monitoring visits has occurred.

The infusion will be provided in an opaque bag to obscure the bag, since SAB-301 may develop bubbles similar to what is seen with IGIV, if the product is agitated. This process has been used in other studies (INSIGHT influenza IVIG) and was successful in maintaining blinding of the study team.

[figure not shown]

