SAB-301 has no binding to human or rabbit tissues in standard tissue cross-reactivity studies (Report A398-14). As SAB-301 is a human IgG, there is no ideal animal for pre-clinical toxicity testing as any animal model will see SAB-301 as a foreign protein. Therefore, the safety or toxicity of SAB-301 in animals may not fully predict the safety or toxicity in humans. With acknowledgment of these limitations, however, the animals used were standard preclinical species. In preclinical toxicity studies in a New Zealand White Rabbits model with doses up to 370 mg/kg, no drug-related effects were observed for clinical observations, body weight, hematology and coagulation parameters, and gross necropsy findings (Report M207-15). All animals survived until their scheduled sacrifices. A 2 and 3.9-fold increase in globulin (GLO) was observed in the males treated with SAB-301 at 50 and 370 mg/kg, respectively, compared with the controls on Day 3. The GLO level was also increased, 1.4- and 4.4- fold, respectively in the females in the 200 and 370 mg/kg groups, compared with the controls. Correlatively, the albumin to globulin ratio was decreased, while total protein was increased in these animals. By Day 50, the globulin, albumin to globulin ratio, and total protein returned to normal after 7

weeks recovery period. The increase in globulin level is considered to be test article-related, but could represent an increase due solely to the presence of SAB-301 in the blood. Evaluation on the plasma drug levels, toxicokinetics, and histopathology are in progress.

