5.2 Formulation, Packaging and Labeling

5.2.1 SAB-301

SAB-301 is a purified human immune globulin G (hIgG) polyclonal antibody designed to specifically bind to the MERS-CoV spike (S) protein, a component of the virion membrane that is responsible for binding of the virus to the host cell. The hIgG is purified from the plasma of immunized transchromosomal (Tc) bovines that were immunized with a recombinant MERS spike protein. The vaccine was produced in insect cells. SAB-301 is purified hIgG in a sterile liquid formulated in 10 mM glutamic acid monosodium salt, 262 mM D-sorbitol, 0.05 mg/mL Tween 80, pH 5.5. The drug product will be administered intravenously and will be diluted in saline per the clinical protocol.

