5.2.2 Saline Control

Subjects randomized to the control infusion will receive normal (0.9%) saline in approximately the same volume as they would have received if randomized to the active arm.

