6.3.8.3 Laboratory Testing

The following clinical laboratory tests will be performed and documented:

- CBC with differential
- Reticulocyte count

- PT/PTT
- Chemistry panel
- Urinalysis
- Quantitative Immunoglobulins (IgG level)
- Rheumatoid factor
- Urine biomarkers
- Stored serum for pharmacokinetics (8 mL blood)

(Elements of each panel are listed in Section 7.1.1)

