7 MEASURES OF SAFETY, EFFICACY, AND COMPLIANCE

7.1 Safety Evaluations

7.1.1 Laboratory Evaluations

All laboratory evaluations (except reference endpoint assays) will be performed at the NIH clinical laboratory (CLIA-certified). Blood samples will be collected from subjects as noted in the schedule of assessments. Abnormal labs thought to be erroneous may be repeated once.

On the designated days, the following laboratory tests will be performed:

- CBC with differential: white cell count (to include absolute neutrophil, and lymphocyte counts), hemoglobin, hematocrit, and platelet count
- Reticulocyte count
- Prothrombin Time (PT) and Partial Thromboplastin Time (PTT)
- Chemistry panel: Na, K, total CO₂, BUN, creatinine, glucose, ALT, AST, total bilirubin, LDH, CPK, and estimated GFR by the CKD-EPI equation)
- Routine urinalysis (includes protein, glucose, ketones, hemoglobin, urobilinogen, leukocyte esterase, nitrite, pH, specific gravity, RBCs, WBCs)
- Urine biomarkers (quantitative albumin, quantitative protein, β 2-microglobulin, and creatinine)
- Serum or urine pregnancy test (females of childbearing potential only)
- Quantitative Immunoglobulins (IgG level)
- Rheumatoid factor

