11.2 Recording/Documentation

At each contact with the subject, information regarding AEs will be elicited by appropriate questioning and examinations and will be immediately recorded on a source document. Source documents will include: progress notes, laboratory reports, consult notes, phone call summaries, survey tools, and data collection tools. Source documents will be reviewed in a timely manner by the research team. All reportable AEs that are identified will be recorded in CRIMSON. The start date, the stop date, the severity of each reportable event, and the PI's judgment of the AEs relationship to the study agent/intervention will also be recorded in CRIMSON.

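### Post-dose IgG results reach the blinded team by default, although the study drug is itself IgG and no stated rule or endpoint uses the level; at 50 mg/kg this permits better-than-chance guessing of allocation

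*Combined protocol and SAP*

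**What the plan says.** Section 5.1 states that "Study participants and study team (PI and associate Investigators and study staff) will be blinded throughout the entire study". It adds that "The study team will be unblinded after the Study Day 90 visit, all laboratory (and immunogenicity) results are available"; that sentence sets when the code is released and does not hold back laboratory values before then. The protections described are an opaque bag (5.1, 5.3), a covered drip chamber (5.3) and a pharmacy log kept from the investigators (5.5). These deal with appearance and records.

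On the product, 5.2.1 says "SAB-301 is a purified human immune globulin G (hIgG) polyclonal antibody". On the control, 5.2.2 says "Subjects randomized to the control infusion will receive normal (0.9%) saline in approximately the same volume".

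The Day 3 laboratory list (6.3.8.3) includes "Quantitative Immunoglobulins (IgG level", and the same test appears at baseline and on Days 7, 21, 42 and 90 (Table 3 and the visit sections of 6.3). Table 3 places it under safety laboratory. Section 7.1.1 says "All laboratory evaluations (except reference endpoint assays) will be performed at the NIH clinical laboratory (CLIA-certified", and the IgG level is in the list that follows. Section 11.2 says "Source documents will include: progress notes, laboratory reports, consult notes", and has the research team review source documents promptly.

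The pausing rules (12.7), the escalation rules (12.8), the criteria for slowing or stopping an infusion (5.3) and the endpoints (12.10) do not mention the IgG level. The nearest item is rheumatoid factor in 12.8, which is a separate test. The only rule based on an immunoglobulin level is IgA deficiency, an exclusion criterion applied before dosing.

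**The concern.** The plan takes care to hide what the infusion looks like but leaves in view a serial measurement of the same class of protein that it infuses. A subject given saline should show a flat IgG; a subject given a large dose of IgG should show a rise. The team that elicits symptoms, grades events and judges relatedness would receive those values during follow-up.

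Two things are exposed. One is the elicitation and grading of subjective adverse events after Day 3, which enter the primary comparison with placebo (12.10.1). The other is the PI's causality rating (11.2), which feeds some of the safety rules. At the target dose there are only two saline subjects beside eight active ones, so a few influenced judgements could alter the comparison in that cohort.

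**Working it through.** The plan gives no figure for this, so there is none to reproduce. The question is how informative the IgG result is.

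**Inputs from the protocol**
- Cohort 6: 50 mg/kg, eight SAB-301 and two saline (Table 1).
- Human IgG of 7 to 16 g/L (1.1); midpoint 11.5 g/L.
- IgG at Day 0, Day 3 and Day 7 (Table 3).

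**Assumptions not in the protocol**
- Plasma volume 40 to 50 mL/kg.
- 50 to 75% of the dose still in plasma at Day 3, with the same rise used at Day 7. This is generous, since Day 7 should be no higher.
- Within-person CV, assay included, of 3 to 8%.

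**Step 1: expected rise.** Rise = dose / plasma volume × fraction retained.
- Low: 50/50 × 0.50 = 0.50 g/L.
- High: 50/40 × 0.75 = 0.94 g/L.
- As a share of baseline: 4.3 to 8.2% of 11.5 g/L, 7.1 to 13.4% of 7 g/L, 3.1 to 5.9% of 16 g/L.

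**Step 2: noise.** For the mean of two post-dose values minus one baseline value, SD = CV × 11.5 × √(1/2 + 1).

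**Step 3: discrimination.** The probability that an active subject's change exceeds a saline subject's is Φ(rise / (SD × √2)). The probability that the two saline subjects have the two smallest of ten changes is the integral of 2φ(x)Φ(x)[1 − Φ(x − d)]⁸ over x, with d = rise/SD. Blind guessing gives 1/45 = 0.02.

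| CV | SD of change (g/L) | Active ranks above saline: rise 0.50 / 0.94 | Both saline subjects lowest: rise 0.50 / 0.94 |
|---|---|---|---|
| 3% | 0.42 | 0.80 / 0.94 | 0.22 / 0.60 |
| 5% | 0.70 | 0.69 / 0.83 | 0.10 / 0.27 |
| 8% | 1.13 | 0.62 / 0.72 | 0.06 / 0.13 |

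Worked cell (CV 5%, rise 0.50): SD = 0.05 × 11.5 × 1.225 = 0.704; 0.50 / (0.704 × 1.414) = 0.50; Φ(0.50) = 0.69.

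**Sensitivity to baseline, CV 5%.** At 7 g/L the ranking probability is 0.80 to 0.94; at 16 g/L it is 0.64 to 0.75.

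**Lower doses, same method, baseline 11.5 g/L.** At 20 mg/kg the rise is 0.20 to 0.375 g/L and the ranking probability 0.55 to 0.73 (0.58 to 0.65 at CV 5%). At 10 mg/kg it is 0.52 to 0.62. The signal is concentrated in cohort 6.

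**Step 4: which rules depend on judgement.** Two of the seven pausing criteria (related SAE; three subjects with the same related Grade 2 or higher event) and three of the seven escalation criteria (related SAE; same related Grade 3 or higher event; 30% with the same related Grade 2 or higher event) need attribution to study drug: 5 of 14.

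**The case against.** Much can be said on the other side, and several parts of it stand.

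- **Escalation.** A reader might infer that the leak biases dose escalation. Cohort 6 is the last cohort, so no escalation decision follows it. A decision does follow cohort 5, but at 20 mg/kg the signal is weak. What remains in cohort 6 is the pausing rules and the provision in 12.8 for DSMB review whenever a criterion is met.
- **Attribution.** A reader might suppose that the safety rules rest mostly on relatedness. Only 5 of 14 criteria do; the others use events or laboratory values irrespective of attribution. The medical monitor can also obtain the unblinded scheme (12.7), and the DSMB sees unblinded data (12.8).
- **Primary endpoint.** It counts adverse events whether or not judged related (11.3, 12.10.1), so causality ratings do not reach it. Only elicitation and grading could. The first post-dose IgG is on Day 3, too late to affect assessment of reactions on Days 0 and 1.
- **Rabbit data.** Section 1.1 reports "A 2 and 3.9-fold increase in globulin (GLO) was observed in the males treated with SAB-301 at 50 and 370 mg/kg, respectively", and it is tempting to expect a doubling in humans. The same paragraph gives only a 1.4-fold rise in females at 200 mg/kg. The rabbit result supports the idea that infused product registers in blood; it does not size the human effect, and the calculation does not use it.
- **Usefulness.** IgG may have descriptive safety value without a numerical rule. That stands: the documents support saying that no stated rule or endpoint uses the level, not that measuring it is pointless.
- **Text not available.** Sections 7.1.3, 7.2 and the start of 8.1.1 were not in the text reviewed, and the Safety Review and Communications Plan is a separate document. Either might already restrict IgG reporting. That the team sees the values is an inference from 7.1.1 and 11.2, though a natural one.

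These points shrink the concern. None shows that the result is masked or that any listed rule needs it.

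**Conclusion.** The point holds as a minor, inexpensive gap in protecting the blind. At 50 mg/kg the blinded team could guess allocation better than chance: a pairwise ranking probability of 0.62 to 0.94 (0.69 to 0.83 at CV 5%), and a 0.06 to 0.60 chance (0.10 to 0.27 at CV 5%) that the two saline subjects show the two smallest changes, against 0.02 by guessing. These figures rest on the assumed plasma volume, retention and CV, and on a baseline of 11.5 g/L.

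The stronger reading, that the team could tell who received saline, is not supported: at CV 5% and this baseline, picking the two smallest changes would be wrong about three times in four or more often. The size of any resulting bias in adverse event grading or causality cannot be derived from the documents.

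**What to change.** State in 5.1 and 7.1.1 that post-dose quantitative IgG results are withheld from the blinded team until unblinding, and are available meanwhile on request to the medical monitor or another unblinded party. Leave rheumatoid factor visible, because 12.8 uses it. If the Safety Review and Communications Plan or another section already does this, a cross-reference in 5.1 is enough.

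Samples and assays are unchanged, no pausing or escalation criterion loses an input, and this route to guessing falls to chance (0.50 for a pair, 1/45 for both saline subjects). The cost is a restriction on laboratory reporting and one inconvenience: a clinician who wants an IgG value during the study must ask for it through the unblinded party.

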5.2 Formulation, Packaging and Labeling

5.2.1 SAB-301

SAB-301 is a purified human immune globulin G (hIgG) polyclonal antibody designed to specifically bind to the MERS-CoV spike (S) protein, a component of the virion membrane that is responsible for binding of the virus to the host cell. The hIgG is purified from the plasma of immunized transchromosomal (Tc) bovines that were immunized with a recombinant MERS spike protein. The vaccine was produced in insect cells. SAB-301 is purified hIgG in a sterile liquid formulated in 10 mM glutamic acid monosodium salt, 262 mM D-sorbitol, 0.05 mg/mL Tween 80, pH 5.5. The drug product will be administered intravenously and will be diluted in saline per the clinical protocol.

5.2.1.1 Label

Figure 1: SAB-301 Vial Label

5.2.1.2 Storage

Store SAB-301 at 2-8 C

5.2.2 Saline Control

Subjects randomized to the control infusion will receive normal (0.9%) saline in approximately the same volume as they would have received if randomized to the active arm.

5.3 Dosing and Administration

The NIH clinical center guidelines for administration of a standard human 10% IGIV (10g/100mL) are for the initial rate to be 0.6 mL/kg/hr, and the rate can be increased gradually to a maximum of 4.8 mL/kg/hr, if tolerated.

SAB-301 will be prepared in the following dilutions:

- Cohorts 1&2: will be prepared as a solution 1mg/1ml (0.1% solution by weight), which is 1/100th the concentration of standard human IGIV (e.g Gammunex).
- Cohorts 3&4 will be prepared as a solution 4mg/1ml (0.4% solution by weight), which is 1/25th the concentration of standard human IGIV.
- Cohorts 5&6 will be prepared as a solution 20mg/1ml (2% solution by weight), which is 1/5th the concentration of standard human IGIV.

The dose of study drug will be calculated based on the subject's dose cohort and weight (up to a maximum weight of 100 kg). The NIH pharmacy will prepare a bag containing the dose of SAB-301 plus as much normal (0.9%) saline as is needed to reach the above listed concentrations. The infusion will be provided in an opaque bag to obscure the bag (as the

SAB-301 may develop bubbles like IGIV if agitated). The drip chamber will also be covered, but accessible if needed by nursing staff for verification of flow rate, etc.

Table 2: Dosing and Administration

Cohort	Dose (mg/kg)	Concentration	Start Rate (mL/kg/hr)	End Rate (mL/kg/hr)	Start Rate (mg/kg/hr)	End Rate (mg/kg/hr)	Proportion of Human IVIG Rate	Duration (mins) (approx.)
1	1	1 mg/mL (0.1 %)	0.5	2	0.5	2	1/120 th - 1/240 th	53
2	2.5	1 mg/mL (0.1 %)	0.5	3	0.5	3	1/120 th - 1/160 th	90
3	5	4 mg/mL (0.4 %)	0.5	2	2	8	1/30 th - 1/60 th	60
4	10	4 mg/mL (0.4 %)	0.5	3	2	12	1/30 th - 1/40 th	85
5	20	20 mg/mL (2 %)	0.5	1	10	20	1/6 th - 1/12 th	70
6	50	20 mg/mL (2 %)	0.5	2	10	40	1/6 th - 1/10 th	97

The infusion will be started at of 0.5 mL/kg/hr, escalating by 0.5 mL/kg/hr increments every 15 minutes to a maximum specified above (end rate).

It is anticipated that the infusion is prepared the morning of the infusion. Since the study drug has been shown stable for 24 hours when mixed in saline, the infusion should be started within 12 hours of preparation in order to assure completion within 24 hours.

The dosing of an individual subject will be slowed and or stopped (depending on clinical assessment) for the following:

- hypotension (systolic or mean blood pressure decreases by 20 mmHg)
- shortness of breath, wheezing, or desaturation
- pain, tenderness, erythema, or swelling around the infusion site.
- fevers, chills
- Other adverse reactions not specified, that are concerning for infusion related adverse events.

After clinical assessment, and resolution or improvement of the event of concern, the infusion may be resumed. If the event is not resolving in a reasonable amount of time, the infusion will not be resumed.

However, in order to establish absolute criteria for stopping – the treatment should be immediately stopped should any of the following occur:

- Profound hypotension (systolic blood pressure < 80 mmHg)
- Severe shortness of breath, wheezing, or sustained (i.e., ≥ 10 seconds) oxygen saturation < 90% on room air
- Severe (Grade ≥ 3) local infusion site reactions, including pain, tenderness, erythema, or swelling as defined in the protocol-specified toxicity grading scale
- Body core temperature exceeding 38.5°C
- Suspected sepsis
- Severe chest pain
- Suspected anaphylaxis

The subject's actual time of drug administration will be recorded in the source documents.

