7.1.2 Physical Examinations

A brief physical examination will be conducted at screening to ensure there are no medical conditions that would increase a subject's risk for participation in this study. Symptom-targeted physical examinations will be conducted at all other visits as needed to evaluate new complaints and possible AEs.

small amount and is unlikely to cause AEs related to increased viscosity.

- Aseptic Meningitis Syndrome (AMS) has been reported with IGIV treatments, especially with high doses or rapid infusion. This risk is anticipated to be minimized given the low amount of protein and relatively slow infusion.
- Hemolysis, either intravascular or due to enhanced RBC sequestration, can be seen with human IGIV. This risk is anticipated to be low given the lack of exposure of the cows to RBC antigens.
- Volume overload has been reported with human IGIV. This risk is anticipated to be minimized given the low amount of protein and small total volumes.

There may be unique risks given the animal origin of the IGIV. SAB-301 is a human IgG so it is anticipated the risk with SAB-301 would be less, though there may be residual animal proteins. The most similar product would be an animal polyclonal antibodies to non-human proteins e.g. Horse Heptavalent Botulism Antitoxin.

(<http://www.fda.gov/downloads/BiologicsBloodVaccines/BloodBloodProducts/ApprovedProducts/LicensedProductsBLAs/FractionatedPlasmaProducts/UCM345147.pdf>)

There is the risk of off-target binding of the IVIG. In the worst case, this could cause immune activation (cytokine storm). The tissue cross reactivity assays do not predict any off target binding, and this has not been seen in any other animal IVIG (of Fab fragment) preparations, so this risk is considered negligible.

For Horse Heptavalent Botulism Antitoxin, the most common adverse reactions in all healthy subjects were headache (9%), pruritus (5%), nausea (5%), and urticaria (5%). Other adverse reactions reported in less than 4% of subjects included pyrexia and throat discomfort. All reported adverse reactions were considered mild or moderate. No serious adverse reactions were reported. Two moderate acute allergic reactions that required premature termination of the infusion and treatment were reported. Reactions were predefined as mild if the subject was aware but could tolerate the symptoms. Moderate reactions were predefined as discomfort enough to interfere with normal daily activity.

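### Do Table 2's comparisons with human IVIG for cohorts 5 and 6 misstate the infusion-rate margin in a way that matters?

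*Combined protocol and SAP*

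**What the plan says.** Section 5.3 describes the reference product as a 10% solution (10 g per 100 mL) and says that the guidelines for giving it "are for the initial rate to be 0.6 mL/kg/hr, and the rate can be increased gradually to a maximum of 4.8 mL/kg/hr", if tolerated. For the two highest dose levels it says: "Cohorts 5&6 will be prepared as a solution 20mg/1ml (2% solution by weight), which is 1/5th the concentration of standard human IGIV".

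Table 2 then lists, for each cohort, the concentration, start and end rates in mL/kg/hr, the same rates in mg/kg/hr, a column headed "Proportion of Human IVIG Rate", and a duration marked approximate. From the concentration onward, the rows in question read:

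- Cohort 5 (20 mg/kg): "20 mg/mL (2 %) 0.5 1 10 20 1/6 th - 1/12 th 70"
- Cohort 6 (50 mg/kg): "20 mg/mL (2 %) 0.5 2 10 40 1/6 th - 1/10 th 97"

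Below the table, the infusion is to start at 0.5 mL/kg/hr and rise by 0.5 mL/kg/hr every 15 minutes to the maximum in the end-rate column.

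The discussion of SAB-301 risks (Section 8.1.1) says of aseptic meningitis: "This risk is anticipated to be minimized given the low amount of protein and relatively slow infusion".

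**The concern.** The fraction column is the protocol's only numerical comparison of infusion speed with the reference product, and this is a first-in-human study. Two entries disagree with the rates printed in the same rows. Both belong to the highest dose levels, including the 50 mg/kg target dose. By Table 1 these cohorts hold 20 of the 38 subjects, 16 of them on SAB-301.

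If the fractions were the intended quantity, the listed end rates would be wrong. If the listed rates are intended, the comparison with IGIV is wrong. Because the risk section cites slow infusion as a mitigating factor, a reader could fear that the safety margin had been overstated or that subjects might be infused at an unintended rate.

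The durations also seem uneven. Cohorts 2 and 4 have the same volume per kg and the same rate steps, yet the table gives 90 and 85 minutes.

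**Working it through.** **Inputs (Section 5.3).** Reference IGIV: 100 mg/mL. Its start rate is 0.6 × 100 = 60 mg/kg/hr and its maximum is 4.8 × 100 = 480 mg/kg/hr. SAB-301 doses, concentrations and rates are those in Table 2.

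**Formula.** Start fraction = SAB-301 start rate ÷ 60. End fraction = SAB-301 end rate ÷ 480. Rates are in mg/kg/hr.

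| Cohort | Start rate | Start, computed | Start, stated | End rate | End, computed | End, stated |
|---|---|---|---|---|---|---|
| 1 | 0.5 | 1/120 | 1/120 | 2 | 1/240 | 1/240 |
| 2 | 0.5 | 1/120 | 1/120 | 3 | 1/160 | 1/160 |
| 3 | 2 | 1/30 | 1/30 | 8 | 1/60 | 1/60 |
| 4 | 2 | 1/30 | 1/30 | 12 | 1/40 | 1/40 |
| 5 | 10 | 1/6 | 1/6 | 20 | **1/24** | **1/12** |
| 6 | 10 | 1/6 | 1/6 | 40 | **1/12** | **1/10** |

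Ten of twelve values match exactly, so this is the column's formula. The two that fail are out by 24/12 = 2.0 and 12/10 = 1.2. Other constructions do not rescue them. The ratio of volume rates gives 1/4.8 and 1/2.4. The end rate against the IGIV start rate gives 1/3 and 1/1.5.

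**Direction.** The stated fractions exceed the computed ones (1/12 > 1/24; 1/10 > 1/12). The table therefore shows the infusion as closer to the IGIV maximum than the listed rates put it.

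**Which columns agree with each other?** Rate × concentration: 1 × 20 = 20 (cohort 5) and 2 × 20 = 40 (cohort 6), as printed. Volume = dose ÷ concentration: 20/20 = 1 mL/kg and 50/20 = 2.5 mL/kg. Durations under the 15-minute step rule are:

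- Cohort 5, listed end rate 1 mL/kg/hr: 15 min at 0.5 delivers 0.125; the remaining 0.875 at 1 takes 52.5 min. Total 67.5 min (stated 70).
- Cohort 6, listed end rate 2 mL/kg/hr: 45 min at 0.5, 1 and 1.5 delivers 0.75; the remaining 1.75 at 2 takes 52.5 min. Total 97.5 min (stated 97).

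Working back from the printed fractions instead:

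- Cohort 5: 480/12 = 40 mg/kg/hr, or 2 mL/kg/hr. Duration 45 + (0.25/2) × 60 = 52.5 min.
- Cohort 6: 480/10 = 48 mg/kg/hr, or 2.4 mL/kg/hr, which steps of 0.5 do not land on. Duration 60 + (1.25/2.4) × 60 = 91.25 min.

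The stated 70 and 97 minutes fit the listed rates and not the fractions.

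**Cohorts 2 and 4.** Both have 2.5 mL/kg and an end rate of 3 mL/kg/hr. The first 75 min deliver 1.875; the remaining 0.625 at 3 takes 12.5 min. Total 87.5 min. The stated 90 and 85 are each 2.5 min away, the same gap as cohort 5's 70 against 67.5.

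**What depends on the fraction?** The criteria for slowing or stopping an infusion (Section 5.3) are clinical signs. The dose justification (Section 5.4) compares doses with the 370 mg/kg nonclinical maximum. The pausing and escalation rules (Sections 12.7 and 12.8) use adverse events and laboratory findings. The study-size calculation (Section 12.9.1) uses assumed event rates and cohort sizes. None of these uses the fraction.

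**The case for a change.** The best case for acting is that this is a true contradiction that rounding cannot explain. It does not even depend on the 480 figure. Cohorts 5 and 6 share a concentration and the end rate doubles, so against any fixed comparator the fraction must double, yet the table moves only from 1/12 to 1/10, a 1.2-fold rise. Cohorts 3 and 6 both end at 2 mL/kg/hr with a five-fold difference in concentration, so cohort 3's 1/60 implies 1/12 for cohort 6. The approximate label is on the duration column, not this one. The errors fall at the highest doses, and a correction costs almost nothing.

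All the arithmetic stands; the consequence does not follow. A dosing error would require someone to ignore the explicit rates in the same row, and the instruction that names the end-rate column, and work back from a descriptive fraction. The count of 20 subjects describes who is in the cohorts, not whose infusion would change. The risk section cites no fraction, and its qualitative statement about slow infusion holds under either set, since both put the end rate at no more than one tenth of the IGIV maximum. The duration point falls away: a gap of 2.5 minutes cannot count as agreement in cohort 5 and as error in cohorts 2 and 4, in a column marked approximate.

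**Conclusion.** This is a clerical slip in two descriptive cells, and no change to the plan follows. The end-rate fractions for cohorts 5 and 6 are printed as 1/12 and 1/10, where the listed rates give 1/24 and 1/12. All start fractions and every fraction for cohorts 1 to 4 are consistent. The printed values understate the margin below the IGIV maximum rate, so they do not make the infusion look safer than the listed rates imply.

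The conclusion assumes that the infusion follows the end-rate column, as Section 5.3 instructs. The agreement of the volume-rate, mass-rate and duration columns points to the two fractions as the odd entries. The documents do not formally settle what was intended. The sponsor must reconcile the rows, and no rate is suggested here. Reconciling the fractions to the listed rates would alter no subject's infusion, no endpoint or decision rule, and nothing the trial can conclude.
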